## **11. SAMPLE SIZE JUSTIFICATION**

Assuming a difference in mean visual acuity between groups of 0.05 logMAR^2 and a pooled standard deviation of 0.1 logMAR, the study would require a sample size of: 69 subjects for each group (total sample size of 138 subjects), to achieve a power of 90% and alpha = 0.05.

There is significant uncertainty in the assumptions for mean difference between groups and pooled standard deviation. Therefore, blinded sample size re-estimation is planned. One interim analysis will be conducted after enrollment of 30 subjects in each group (60 subjects total) to re-estimate the sample size.

One interim analysis will look at the variability in each group (biostatistician should be blinded to the groups). Using these values, the required sample size will be re-estimated.

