### 3. GENERAL INFORMATION

Objective	To compare binocular visual outcomes with light adjustable lens (LAL) vs. Clareon monofocal/toric IOL when both are targeting mini-monovision (-0.75 ~ -1.00 D in the non-dominant eye).  The hypothesis is that the Clareon monofocal/toric IOL with mini-monovision will provide non-inferior binocular distance vision compared to LAL mini-monovision (non-inferiority margin: 0.1 logMAR).
Test Article(s)	The Clareon™ Monofocal Intraocular Lens (Toric and Non-Toric) The Light-Adjustable Lens™
Sample size	138 subjects total (69 in each group)
Study Population	Age-related Cataract patients with $\geq 0.75$ D corneal astigmatism and without previous experience of monovision $> -1.00$ D offset.
Number of sites	One
Study Design	Single center, multi-surgeon, prospective, randomized, comparative study.
Masking	None.
Variables	Primary: Binocular corrected distance visual acuity (CDVA), 3-months postop.  Secondary: 

• Binocular uncorrected distance visual acuity (UDVA), 3-months postop.

• Binocular distance-corrected intermediate visual acuity (DCIVA) at 66cm, 3-months postop.

• Binocular uncorrected intermediate visual acuity (UIVA) at 66cm, 3-months postop.

• Monocular corrected distance visual acuity (CDVA), 3-months postop.

- Monocular uncorrected distance visual acuity (UDVA), 3-months postop.
- Monocular distance-corrected intermediate visual acuity (DCIVA) at 66cm, 3-months postop.
- Monocular uncorrected intermediate visual acuity (UIVA) at 66cm, 3-months postop.

Exploratory:

- Binocular distance-corrected near visual acuity (DCNVA) at 40cm, 3-months postop.
- Binocular uncorrected near visual acuity (UNVA) at 40cm, 3-months postop.
- Monocular distance corrected defocus curve at 3 months post-op for both eyes in LAL group and dominant eye for Clareon group.
- Binocular defocus curve at 3 months post-op (dominant eye: plano corrected, non-dominant: -1.00D)
- Manifest refraction (MRSE, residual sphere, and residual astigmatism) at postoperative day 17-28 and at 3 months post-op.
- Patient reported spectacle usage questionnaire (PRSIQ) at postoperative day 17-28 and at 3 months post-op
- Total ocular, corneal and internal HOA and SA with iTRACE for both eyes in LAL group and dominant eye for Clareon group (Objective depth of focus measurement with iTRACE for each eyes in both groups)

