## 7. SUBJECTS

### 7.1. *Subject Population*

Eligible test subjects will be adult normal astigmatic ( $\geq 0.75$ D corneal astigmatism) cataract patients presenting for cataract surgery who are considered appropriate candidates for intraocular lens implantation.

A total of 138 subjects at one site will be enrolled (69 per group). Both eyes of a subject must be enrolled. Subjects must meet the inclusion criteria. Prior to enrollment, subjects will be provided information on the study and asked to sign a patient information and consent form to participate. The patient information and consent form will be approved by an appropriate ethics committee.

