##### **10.2.1. Within-treatment Changes**

For variables measured on a continuous scale, these summaries will include the sample size, as well as the mean, standard deviation, median, minimum, and maximum. For variables measured on a categorical scale, summaries will provide the number and percentage of eyes in each category. These summaries will be provided for all eyes completing the study.

Differences between parametric variables will be compared using a two-sample t-test. Differences between categorical variables will be compared using the 2-sample test for equality of proportions.

For non-inferiority testing, if the upper boundary of the 95th confidence interval is not greater than 0.1 logMAR, non-inferiority will be claimed.

The step-down methodology will be used on the non-inferiority endpoints in the following order:

- 1) Binocular CDVA
- 2) Binocular DCIVA
- 3) Binocular UDVA
- 4) Binocular UIVA

The correlation of total ocular and internal HOAs (especially SA) with monocular DCIVA will be evaluated using regression modelling. Findings from these models will provide an indication of whether any HOAs are statistically significantly associated with post-op DCIVA, and the strength of any such association.

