### **10.3. General Statistical Considerations**

The statistical analyses will be performed using R, version 4.2.2 or higher. Any statistical tests of hypotheses will employ a level of significance of alpha=0.05.

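### The 69 per group said to give 90% power is a one-sided 0.05 figure; under the plan's 95% confidence interval rule, power is about 83%, and lower with any loss of subjects

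*Combined protocol and SAP*

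**What the plan says.** Section 3 sets a "non-inferiority margin: 0.1 logMAR" for Clareon against LAL. Section 11 derives the sample size from two planning values, "Assuming a difference in mean visual acuity between groups of 0.05 logMAR" and "a pooled standard deviation of 0.1 logMAR", and concludes that the study needs "69 subjects for each group (total sample size of 138 subjects), to achieve a power of 90% and alpha = 0.05". It does not say whether that alpha is one-sided or two-sided.

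The decision rule is in Section 10.2.1: "if the upper boundary of the 95th confidence interval is not greater than 0.1 logMAR, non-inferiority will be claimed". It applies to binocular CDVA first and then, by step-down, to three further binocular endpoints. Section 10.3 adds "Any statistical tests of hypotheses will employ a level of significance of alpha=0.05", again without sidedness.

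On numbers, Section 7.1 states: "A total of 138 subjects at one site will be enrolled (69 per group"), which is exactly the Section 11 requirement. Section 10.1 restricts efficacy analysis to eyes with uncomplicated completed surgery. Section 18.2 replaces only subjects lost before surgery, and Section 18.3 does not replace subjects terminated for a severe adverse event. Section 11 also plans a blinded re-estimation of sample size from the observed variability, after 30 subjects per group.

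**The concern.** A 95% confidence interval not described as one-sided is normally two-sided. Requiring its upper limit to lie within the margin is then a test at one-sided 0.025. If the sample size was computed at one-sided 0.05, the trial is sized for an easier test than the one it will apply, and the stated 90% power is not delivered.

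If the interval was meant as a one-sided 95% bound, the power is right, but the trial accepts a 5% chance of wrongly claiming non-inferiority at the margin. That is the error rate of a two-sided 90% interval, and the plan does not say so. Either the power or the interval is mis-stated. The same ambiguity runs through all four step-down endpoints, and a result could pass on one reading and fail on the other.

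A second, smaller point is that there is no room for loss. Follow-up runs to day 90 and some eyes are dropped from efficacy by design, so 69 evaluable per group requires every operated subject to be evaluable.

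**Working it through.** **Inputs.** Margin 0.1 logMAR (Section 3); assumed difference 0.05 logMAR, SD 0.1 logMAR, power 90% and alpha 0.05 (Section 11); two-sample t-test (Section 10.2.1); 1:1 allocation (Section 8.3). Section 11 gives no direction for the 0.05. For a non-inferiority calculation it must mean Clareon is worse by 0.05, which leaves 0.1 − 0.05 = 0.05 to the margin.

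**Formula.** n per group = 2(z_α + z_β)² × SD² / (margin − difference)². Here SD²/(margin − difference)² = 0.01/0.0025 = 4, so n = 8(z_α + z_β)².

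**Reproducing the plan's figure (one-sided 0.05).** 8 × (1.645 + 1.282)² = 68.5, so 69. This matches. Power at 69 is 90.2% (normal) or 89.9% (noncentral t).

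**Under the two-sided 95% interval (one-sided 0.025).** 8 × (1.960 + 1.282)² = 84.06, so 85. With the noncentral t it is 86.

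**Other routes to 69.** Assuming no true difference gives 18 per group (one-sided 0.05) or 22 (one-sided 0.025). A superiority calculation on a difference of 0.05 gives 69 one-sided and 85 two-sided, because the distance is again 0.05. Every route tried that returned 69 used a one-sided alpha of 0.05.

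**Power of the stated rule at 69 per group.** The standard error is 0.1 × √(2/69) = 0.01703, and 0.05/0.01703 = 2.937. Power = Φ(2.937 − 1.960) = Φ(0.977) = 83.6%; the noncentral t gives 83.0%.

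**Effect of loss.** The documents give no rate, so 5% and 10% are assumptions. 69 × 0.95 = 65.6 and 69 × 0.90 = 62.1, taken as 65 and 62.

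| Evaluable per group | One-sided 0.025, normal | One-sided 0.025, t | One-sided 0.05, t |
|---|---|---|---|
| 69 | 83.6% | 83.0% | 89.9% |
| 65 (5% loss) | 81.3% | 80.8% | 88.3% |
| 62 (10% loss) | 79.5% | 78.9% | 86.9% |
| 86 | 90.6% | 90.3% | 94.8% |

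**Where the two readings disagree.** With 69 per group and an SD of 0.1, the largest passing observed difference is about 0.1 − 1.960 × 0.01703 = 0.067 logMAR for the two-sided 95% interval, and 0.1 − 1.645 × 0.01703 = 0.072 for the one-sided 95% bound. An observed difference between these values is non-inferior on one reading only.

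**Re-estimation.** Section 11 names no alpha for this step. If the same formula is reused with a new SD, the result is 68.5/84.06 = 0.81 of what the 95% interval needs, about 19% too low whatever the SD.

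**The case against.** The strongest reply is that the documents never state sidedness. Only the upper bound matters for non-inferiority. If it is a one-sided 95% bound, Sections 10.2.1, 10.3 and 11 agree with each other and 69 gives 90%. That reading is possible and the text does not exclude it. It is not the ordinary reading of a 95% confidence interval, however, and it leaves an unstated 5% one-sided error. It therefore changes which statement needs correcting, not whether one does.

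It can also be said that the shortfall is modest beside the uncertainty Section 11 admits. At 69 per group and one-sided 0.025, 90% power returns (normal approximation) if the SD is about 0.091 or the true difference about 0.045, and at a true difference of zero power exceeds 99.9%. This is correct, and the 83% is conditional on the planning values. But the stated 90% is conditional on the same values and should hold under them.

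The re-estimation may change the sample size, so 83% need not be the final power. It works on variability, though, and does not by itself correct the alpha.

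Finally, the loss rates are not in the documents. This stands: the figures at 5% and 10% only illustrate the effect, and the missing allowance is secondary to the alpha mismatch. It also remains that a positive result under the two-sided 95% rule would be valid at 2.5% one-sided error. On that reading the damage is to power, not to the claim.

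**Conclusion.** The concern holds. The 69 per group comes from a one-sided alpha of 0.05, whereas the decision rule, as ordinarily read, is a one-sided 0.025 test. Under the plan's own difference, SD and margin, power is about 83% instead of 90%, so the chance of missing true non-inferiority is about 17% instead of 10%. It reaches about 21% with an assumed 10% loss.

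The one reading that restores 90% trades the power shortfall for an undeclared 5% one-sided error, and even then an assumed 10% loss brings power to about 87%. Because the primary decision threshold depends on which reading applies, this must be settled before outcome data are seen.

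**What to change.** 1. **Section 10.2.1.** State that non-inferiority is claimed when the upper limit of the two-sided 95% confidence interval (one-sided alpha 0.025) for mean logMAR, Clareon minus LAL, is at or below 0.1.
2. **Section 11.** State the one-sided alpha of 0.025 and the direction of the assumed 0.05 difference. Give power as about 83% with 69 evaluable per group, and about 79% if 10% are lost, labelled as an assumed rate. Say that 69 is the number enrolled and makes no allowance for loss.
3. **Re-estimation.** Require it to use one-sided 0.025.
4. **If one-sided 0.05 is truly intended.** Call the bound the upper limit of a two-sided 90% interval, state the 5% one-sided error, and keep Section 11 at about 90% with 69 evaluable.

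The cost is wording and, under items 1 to 3, a less favourable stated power. No extra patients are required. If the sponsor prefers to keep 90% under the 95% interval, the need is 86 evaluable per group (172 in total, 34 more than planned), or 96 enrolled per group with an assumed 10% loss (86/0.9 = 95.6).

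### Section 11's re-estimation is called blinded but needs the data split by arm, sets no minimum size, and cannot address the uncertain mean difference that it cites

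*Combined protocol and SAP*

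**What the plan says.** Section 11 sizes the trial at 69 per group: "Assuming a difference in mean visual acuity between groups of 0.05 logMAR" and "a pooled standard deviation of 0.1 logMAR", "to achieve a power of 90% and alpha = 0.05". It then gives the reason for a re-estimation: "There is significant uncertainty in the assumptions for mean difference between groups and pooled standard deviation". It calls the re-estimation blinded and places it after 30 subjects per group (60 in total) have enrolled. The method is two sentences. The first is "One interim analysis will look at the variability in each group (biostatistician should be blinded to the groups"). The second is "Using these values, the required sample size will be re-estimated".

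The section gives no formula, minimum size or alpha for the recalculation. It does not say whether the 0.05 difference stays fixed, how the data are split or coded, or whether group means are withheld. Sections 3 and 7.1 give 138 subjects as the enrollment, without calling it a minimum. The primary endpoint is binocular CDVA at 3 months (section 8.1), measured at Visit 8. Section 10.2.1 sets the decision rule: "if the upper boundary of the 95th confidence interval is not greater than 0.1 logMAR, non-inferiority will be claimed".

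**The concern.** Three parts of the rule do not fit together.

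- **Label and method.** A blinded variance estimate treats all subjects as one sample. An SD per group requires someone to divide the data by arm. Blinding the biostatistician to the groups can then mean only that the arm labels are hidden.
- **No floor.** The size is recalculated from an SD estimated on at most 60 subjects. As written, a low estimate may shrink the trial. The four-step non-inferiority sequence in section 10.2.1 uses the same subjects.
- **Reason and remedy.** The section names two uncertain assumptions and offers one remedy. An estimate of variability says nothing about whether the true difference is 0.05, and power is sensitive to that figure.

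The trial is unmasked and run at one centre, so the interim look is a place where a clear written safeguard is cheap and useful.

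**Working it through.** **Inputs.** Margin 0.10 logMAR (section 3); difference 0.05, SD 0.10, power 90%, alpha 0.05, look at 30 per group (section 11); 1:1 allocation (section 8.3). The distance to the margin is 0.10 − 0.05 = 0.05.

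**1. The plan's own figure.** n per group = 2·SD²·(z₁₋α + z₀.₉₀)² / 0.05².

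- One-sided 5%: 2 × 0.01 × (1.645 + 1.282)² / 0.0025 = 68.5, so 69. The plan's figure reproduces.
- One-sided 2.5%: 2 × 0.01 × (1.960 + 1.282)² / 0.0025 = 84.1, so 85.

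So 69 corresponds to one-sided 5%. A two-sided 95% interval corresponds to one-sided 2.5%.

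**2. Size as a function of the interim SD** (same formula, one-sided 5%)

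| Interim SD | 0.08 | 0.09 | 0.10 | 0.11 | 0.12 |
|---|---|---|---|---|---|
| n per group | 44 | 56 | 69 | 83 | 99 |

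**3. Chance of a cut.** The result is 68 or fewer when SD² ≤ 68 × 0.0025 / (2 × 8.564) = 0.009926, that is, SD ≤ 0.0996. With a true SD of 0.10 and 30 per group with data (58 df), the probability is P(χ²₅₈ ≤ 58 × 0.9926) = 0.51. The chance of 50 or fewer is about 6%. If the recalculation used one-sided 2.5%, the chance of falling below 69 would be about 15%.

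**4. What a cut costs the primary endpoint.** The whole procedure was simulated: 30 per group, recalculation from the within-group variance, then a final t-test at one-sided 5%, with true SD 0.10. There were at least 200,000 runs per scenario.

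| Rule | Mean n per group | Power at difference 0.05 | Type I error at difference 0.10 |
|---|---|---|---|
| No floor | 69 | about 89.5% | about 0.052 |
| Floor at 69 | 74 | about 91.6% | about 0.050 |

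Repeated runs moved the powers by 0.1 to 0.2 percentage points.

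**5. A truly blinded estimate.** With all subjects treated as one sample, the expected variance is 0.10² + 0.05²/4 = 0.010625, so SD = 0.1031. Then n = 2 × 0.010625 × 8.564 / 0.0025 = 72.8, so 73 per group. Subtracting 0.05²/4 returns 0.01 and 69 per group. If the true difference were 0, the subtraction would leave 0.009375 and n = 64.2, so 65; a floor at 69 covers that case. With the one-sample estimate and the floor, simulated type I error is about 0.052 to 0.053, much the same as under the present rule.

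**6. What the look cannot address.** At 69 per group and SD 0.10 the standard error is 0.10 × √(2/69) = 0.0170. Power from the noncentral t with 136 df:

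| True difference | 0.04 | 0.05 | 0.06 | 0.07 |
|---|---|---|---|---|
| Distance to margin / SE | 3.52 | 2.94 | 2.35 | 1.76 |
| Power, one-sided 5% | 97% | 90% | 76% | 54% |
| Power, two-sided 95% interval | 94% | 83% | 65% | 42% |

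**The case against.** A reader might infer that the arm difference will be seen at the interim. The documents do not support that. Variability is the only quantity to be examined, no comparison of means is planned, and the biostatistician is to be blinded. Two SDs do not reveal a difference in means. Someone holding data split under masked codes could compute the size of the difference but not its direction. The safeguard is under-specified rather than absent.

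A reader might also argue that coded labels give no protection because Table 15.1 schedules acuity and refraction at Visits 4 to 7 for LAL subjects only. But nothing says that the biostatistician receives those data. Adverse-event monitoring is listed for both groups at those visits, and sections 3 and 8.1 plan the iTrace depth-of-focus measure for each eye in both groups.

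On the floor, a 51% chance of a lower figure is what an estimate centred on the planning SD would give; it exceeds 69 about 46% of the time. Where the SD really is smaller, a smaller trial keeps its power for the primary endpoint: about 90% at SD 0.08 with 44 per group. One can posit a later endpoint in the sequence with SD 0.12 and difference 0.05, whose power would fall from 79% at 69 per group to 62% at 44 (one-sided 5%). Those SDs are assumptions, and the plan claims no power for those endpoints.

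Finally, admitting that the mean difference is uncertain is candid and should stay.

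All of this limits the harm. It does not remove the mismatch between a blinded procedure and SDs by group, supply the missing minimum, or make a variance look informative about the difference.

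**Conclusion.** The point holds as a defect in how the rule is specified, with modest numerical consequences. The procedure is at most label-masked. It permits a final size below 69 per group, about as likely as not if the SD is 0.10 and 30 per group have outcome data. It leaves the uncertainty in the mean difference untouched. For the primary endpoint, the missing floor costs about two percentage points of power (89.5% against 91.6%), and type I error stays near 0.052; both figures assume a test at one-sided 5%. The documents do not show that interim knowledge of the arm difference is planned, or that the sponsor intends to shrink the trial.

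Two details also need settling. The look is triggered by enrollment, while the endpoint is at 3 months, so 60 enrolled does not ensure 60 outcomes. And section 10.2.1 does not say whether its 95% interval is one- or two-sided. If it is two-sided, a recalculation at one-sided 5% would aim at the wrong size.

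**What to change.** Revise section 11 as follows.

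1. **Input and timing.** Give the biostatistician only unlabelled Visit 8 binocular CDVA values, with no other data. Compute the one-sample SD and subtract 0.05²/4 from the variance. Trigger the look on the number of subjects with 3-month data rather than on enrollment.
2. **Floor.** Set the final size per group to the larger of the planned 69 and the recalculated value.
3. **Difference.** State that 0.05 stays fixed and that the look does not address its uncertainty. Keep the statement that it is uncertain, and add the power range in the last table of the working.
4. **Alpha.** State the formula, with the same alpha as the interval in section 10.2.1, and say there whether that interval is one- or two-sided.

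**Cost.** A few sentences of text. The sponsor loses the option to stop below 138. If the SD is 0.10, the average size is about 74 rather than 69 per group, or (74 − 69) × 2 = 10 more subjects than under the rule without a floor. Waiting for 3-month data delays the look. If the interval is two-sided, the recalculation centres on 85 per group; that increase comes from the choice of alpha, not from the floor.

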## **12. CONFIDENTIALITY/PUBLICATION OF THE STUDY**

The existence of this Study is confidential and should not be discussed with persons outside of the Study. Results will be submitted for publication and presentation at national and/or international meetings. A manuscript will be submitted to peer-review journals for publication but there is no guarantee of acceptance.

All study data will be collected on appropriate Case Report Forms (CRFs). No protected health information will be included on the forms. CRFs will be retained in the patient's file for a minimum period of 3 years. Collected information will only be used for purposes of this study and no information will be sold to third parties. The following people will have access to your study records:

- Study Doctor and staff involved with the study
- Study Monitor or Auditor

- Sponsor Company or Research Institution
- Review boards or accrediting agencies
- Other State or Federal Regulatory Agencies

The de-identified data may be shared with other researchers for future analysis.

### **13. QUALITY COMPLAINTS AND ADVERSE EVENTS**

All subjects will be monitored for adverse events over the course of the study. A place to record any adverse event is included on each case report form.

#### ***13.1. General Information***

An Adverse Event (AE) is any untoward medical occurrence in a subject who is administered a study treatment regardless of whether or not the event has a causal relationship with the treatment. An AE, therefore, can be any unfavorable or unintended sign (including an abnormal laboratory finding), symptom, or disease temporally associated with the study treatment, whether or not related to the treatment. In clinical studies, an AE can include an untoward medical occurrence occurring at any time, including run-in or washout periods, even if no study treatment has been administered.

